Condensed and Distributed Robotic Therapy in Spastic Stroke Post Botulinum Toxin
Injection

NCT03321097

Document date Dec, 29, 2016

Spasticity, a common impairment after stroke, has a profound impact on activity and participation for patients. According to the result of our ongoing study, we found Botulinum Toxin A (BoNT-A) injection combined with robot-assisted training is recommended to enhance functional recovery for patients with spastic hemiplegic stroke. However, the optimal program as considering the Robotic Therapy (RT) frequency is unknown.

The aims of this study are to determine and compare the immediate and longer-term effects between condensed and distributed programs of RT following BoNT-A injection in subjects with spastic hemiplegic stroke.

Methods

Participants with stroke will be recruited from a rehabilitation department of tertiary referral hospital. Patients who have spastic hemiplegic stroke are screened for eligibility to join the study. The inclusion criteria will be: (1) clinical and imagine diagnosis of a first or recurrent unilateral stroke ≥ 3 months; (2) upper limb spasticity (modified Ashworth scale of $\geq 1+$ for elbow flexor and/or forearm pronator and/or finger flexor muscles and/or wrist flexor muscles (Bohannon & Smith, 1987); (3) initial motor part of UE of FMA score ranging from 12 to 56, indicating moderate to severe movement impairment (Duncan, Goldstein, Matchar, Divine, & Feussner, 1992; Fugl Meyer, Jaasko, & Leyman, 1975; Park, Wolf, Blanton, Winstein, & Nichols-Larsen, 2008); (4) no serious cognitive impairment (i.e., Mini Mental State Exam score > 20) (Teng & Chui, 1987); (5) age ≥ 18 years ; and (6) willing to provide written informed consent. Participants will be excluded if they are pregnant, or with bilateral hemispheric or cerebellar lesions, sever aphasia, significant visual field deficits or hemineglect, contraindication for BoNT-A injection, treatment with BoNT-A within 4 months before recruitment, any fixed joint contracture of the affected upper limb, or a history of orthopedic or other neurological diseases and/or medical conditions that would prevent adherence to the rehabilitation protocol.

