Participants with will be recruited and randomly assigned to either condensed or distributed RT groups post BoNT-A injection. Each training session included 40 minutes RT, followed by 40-minute functional training. The condensed group will receive 4 sessions per week, for 6 weeks, the distributed group 2 sessions per week, for 12 weeks. Body function and structures outcome measures include Fugl-Meyer Assessment, Modified Ashworth Scale, actigraphy. Activity and participation measures include Wolf Motor Function Test, Motor Activity Log, and Canadian Occupational Performance Measure. In addition, to directly reflect a patient's unique needs and goals, Goal Attainment Scaling will be assessed. Evaluators will be blind to group allocation. The outcome will be measured at pre-treatment, mid-treatment,

post-treatment, and 6-week follow-up.

Data Analysis

To examine the baseline differences among 2 groups, we use the chi-square test and independent-sample t tests to compare participants' baseline characteristics between groups. To examine the therapeutic effects of the RT, we use mixed ANOVA to test the differences within groups across 4 measurement time points (time effect) and to test the differences between groups (condensed intervention group and distributed intervention group) and to test interaction effect between time and group. Pairwise comparison with Bonferroni adjustments is used to examine the differences between measurement time points. All tests are executed using the SPSS software version 25 (International Business Machines Corp., Armonk, NY) at the $\alpha = .05$ level of significance.

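### The aim is to compare the two programs' immediate and longer-term effects, but the plan specifies no condensed-minus-distributed estimate at any post-baseline visit

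*Combined protocol and SAP*

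**What the plan says.** The aims paragraph, ahead of Methods, sets a between-program question: to "determine and compare the immediate and longer-term effects between condensed and distributed programs of RT following BoNT-A injection". It does not define the two time terms.

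Methods gives the courses: "The condensed group will receive 4 sessions per week, for 6 weeks, the distributed group 2 sessions per week, for 12 weeks". Outcomes are taken before treatment, midway, and at "post-treatment, and 6-week follow-up", which makes four visits, three of them after baseline.

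Data Analysis uses a mixed ANOVA with a time effect across the four visits. It also uses the model "to test the differences between groups (condensed intervention group and distributed intervention group) and to test interaction effect between time and group". The follow-up comparisons are then named: "Pairwise comparison with Bonferroni adjustments is used to examine the differences between measurement time points". The only between-group comparison tied to a particular visit is the baseline check by chi-square and t tests. No effect estimate or confidence interval is mentioned.

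**The concern.** The trial exists because the best frequency of robotic therapy is unknown. Answering that takes a difference between programs, with its direction and uncertainty, at the times that matter. As written, the plan can show that the two courses differ somewhere over time. It does not commit anyone to report by how much, in whose favour, or when.

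If the plan is followed literally, a significant interaction leads only to comparisons of visits. Those describe change over time and do not compare the programs. Any between-program contrast would then have to be chosen after the results are seen, across several outcome measures.

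**Working it through.** The documents give no sample size, correlation, standard deviation or effect size, so there is no plan figure to reproduce. Steps 1 to 3 need none of these. Steps 4 and 5 are illustrations on stated assumptions.

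**1. Count of planned comparisons.** Four visits give 4 × 3 / 2 = 6 visit pairs, and none is condensed versus distributed. The interaction has (2 − 1) × (4 − 1) = 3 numerator degrees of freedom. Between-program contrasts named at the three post-baseline visits: 0.

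**2. What the group main effect estimates.** Let the true condensed-minus-distributed differences be (d0, d1, d2, d3) at pre-treatment, mid-treatment, post-treatment and follow-up. The main effect estimates (d0 + d1 + d2 + d3)/4. Randomisation makes d0 = 0 in expectation, so this is (d1 + d2 + d3)/4 = 0.75 × (d1 + d2 + d3)/3, or 75% of the mean post-baseline difference whatever the pattern. Assumed patterns, in units of a difference of size 1:

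| Pattern (pre, mid, post, follow-up) | Main effect |
|---|---|
| (0, 1, 1, 1) | 0.75 |
| (0, 0.5, 1, 1) | 0.625 |
| (0, 0.5, 1, 0) | 0.375 |
| (0, 0, 0, 1) | 0.25 |
| (0, 0.5, 1, −1) | 0.125 |

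In the last row the programs reverse order between post-treatment and follow-up, and the main effect nearly cancels.

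**3. What the interaction tests.** Its signal is the sum of squared deviations of the d's from their mean. Squaring removes the sign, and summing removes the visit. A difference at mid-treatment only, (0, d, 0, 0), therefore contributes to it.

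**4. Illustration of power.** Assumptions: 30 per arm, unit SD, compound symmetry with correlation rho, two-sided 0.05, and a 0.5 SD difference at all three post-baseline visits.
- Main effect: noncentrality = mean(d)² / [2((1 + 3 rho)/4)/n] on F(1, 58). At rho 0.7: 0.375² / (2 × 0.775/30) = 2.72, power 37%.
- Interaction: noncentrality = (n/2) × Σ(d − mean d)² / (1 − rho) on F(3, 174). At rho 0.7: 15 × 0.1875 / 0.3 = 9.375, power 72%.
- Baseline-adjusted contrast at one visit: noncentrality = d² / [2(1 − rho²)/n] on F(1, 57). At rho 0.7: 0.25 / (2 × 0.51/30) = 7.35, power 76%.

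| rho | Main effect | Interaction | Adjusted contrast | 95% CI half-width of contrast (SD) |
|---|---|---|---|---|
| 0.5 | 44% | 48% | 59% | 0.45 |
| 0.7 | 37% | 72% | 76% | 0.37 |
| 0.9 | 32% | 99.7% | 99% | 0.23 |

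With a 0.5 SD difference at mid-treatment only and rho 0.7, the interaction is still significant in 72% of trials. The post-treatment and follow-up contrasts each reject in about 5%, their nominal rate. In that case the interaction reflects neither of the visits that most naturally carry the aim.

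**5. Precision from baseline adjustment.** Under compound symmetry the ratio of variances, adjusted contrast to change-score contrast, is (1 − rho²) / [2(1 − rho)] = (1 + rho)/2, which is 0.75, 0.85 and 0.95 at rho 0.5, 0.7 and 0.9.

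**6. Timing.** Taking the start of training as week 0, and assuming that visits follow each arm's own course, post-treatment falls at week 6 (condensed) and week 12 (distributed). Follow-up falls at 6 + 6 = 12 and 12 + 6 = 18.

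**The case against.** The strongest reply is that the programs are compared. The interaction is a proper randomised test that allows for baseline implicitly, and its power is close to that of a single-visit contrast. In the illustration the contrast is ahead by 11 points at rho 0.5 and by 4 at rho 0.7, and marginally behind at 0.9. This stands. A reader might infer that the plan has no between-program test, or will rest its conclusion on change within each arm. The text supports neither: the group and interaction tests are listed, and nothing says that within-arm change will be taken as evidence between programs. The gap is in estimation.

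Second, the aim names no visits. Reading immediate as post-treatment and longer-term as the 6-week follow-up is an interpretation. What the documents show without it is that no between-program contrast is named at any post-baseline visit.

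Third, the power figures depend on compound symmetry. Under that structure the interaction has the same power for a 0.5 SD difference at any one visit or at all three, and a reader might take this as general. It is not. With first-order autoregressive correlation of 0.85 and a Greenhouse-Geisser correction, simulated power runs from about 73% (constant or follow-up only) to about 83% (mid- or post-treatment only). It remains true that a mid-treatment difference alone can produce significance.

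Finally, statistical software can print between-group differences by visit. That does not make them prespecified, and the plan's sentence confines pairwise comparisons to time points.

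**Conclusion.** The point holds as a gap between aim and analysis. Data Analysis tests the programs against each other but specifies no condensed-minus-distributed estimate or interval at any of the three post-baseline visits. That count and the 75% dilution of the main effect follow from the text and from randomisation alone. The power and precision figures rest on an assumed 30 per arm, an assumed effect and compound symmetry, and the conclusion does not need them.

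The plan is not invalid, and the interaction should stay. The change is worth making because the stated analyses answer the aim poorly when a better one is available from data already planned. Confidence is high on the textual gap and lower on the mapping of the aim's terms to visits, which the sponsor should confirm.

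**What to change.** For each outcome where a mean difference is sensible, fit a repeated-measures model to the post-baseline scores with group, visit, group-by-visit, baseline and baseline-by-visit. Model the within-participant correlation, for example with an unstructured covariance. Report the adjusted condensed-minus-distributed difference with 95% CI at post-treatment (read as immediate) and at the 6-week follow-up (read as longer-term), and say in the SAP that this is how the aim is read. Where a mean difference or a baseline covariate does not fit (check the Modified Ashworth Scale and Goal Attainment Scaling), report a between-group ordinal or rank-based estimate with CI at the same visits. Keep the interaction as supporting evidence, and do not use the group main effect as the treatment comparison.

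State what the visits are timed from. If they follow each arm's course, the contrasts compare the programs at week 6 v week 12, and then at week 12 v week 18, so not at equal time since training began.

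Cost: SAP wording, with visits and scores already planned. Stating the time anchor settles what is being estimated and deserves more thought than the rest. There are also more contrasts to report: seven measures at two visits make 14 if each yields one score, and more if the Modified Ashworth Scale is analysed by muscle group. How to control multiplicity over the two visits is the sponsor's choice, for example a fixed sequence or 0.05/2 = 0.025 each.

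### Seven measures, no primary outcome and no deciding between-program contrast: the only multiplicity adjustment covers time points, not the program comparison that is the trial's aim

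*Combined protocol and SAP*

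**What the plan says.** The aim, stated before the Methods, is comparative: "The aims of this study are to determine and compare the immediate and longer-term effects between condensed and distributed programs". It does not name a measure or a deciding visit, and it does not rank the immediate and longer-term effects.

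The Methods list seven measures in three groups:

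- Three at the level of body function: "Body function and structures outcome measures include Fugl-Meyer Assessment, Modified Ashworth Scale, actigraphy".
- Three for activity and participation: the Canadian Occupational Performance Measure, the Motor Activity Log and the Wolf Motor Function Test.
- Goal Attainment Scaling.

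None is labelled primary. There are four visits: before, midway through and after treatment, and a 6-week follow-up.

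Under Data Analysis, "we use mixed ANOVA to test the differences within groups across 4 measurement time points (time effect"), and also "to test the differences between groups (condensed intervention group and distributed intervention group) and to test interaction effect between time and group". On multiplicity there is one sentence: "Pairwise comparison with Bonferroni adjustments is used to examine the differences between measurement time points". The significance level is common to everything: "All tests are executed using the SPSS software version 25 (International Business Machines Corp., Armonk, NY) at the $\alpha = .05$ level of significance".

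**The concern.** The adjustment sits on the wrong comparison. Differences between visits describe recovery over time, which may occur under both programs. The trial is run to learn whether the programs differ, and the tests that address this (group, and group by time) are repeated over seven measures at .05 with no adjustment, no hierarchy and no decision rule.

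If the seven results are mixed, the plan gives no way to say whether the programs differ. One significant scale out of seven could be reported as the answer or set aside, and either choice would fit the text. The chance that at least one scale reaches significance with no true difference is well above 5%.

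An omnibus interaction on a single measure also does not say at which visit the programs differ, although the aim asks separately about immediate and longer-term effects.

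**Working it through.** The plan states no sample size, power or family-wise error rate, so it has no figure to reproduce.

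**Inputs from the documents.** Seven measures (3 + 3 + 1); two randomised groups; four visits, so the interaction has (2 − 1) × (4 − 1) = 3 numerator degrees of freedom; .05 per test.

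**Assumptions, not in the documents.** One mixed ANOVA per measure with one score each; equal allocation; normal scores; sphericity; equal correlation between measures. The correlation that counts is the one between measures in within-patient change, not in patient level.

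**Step 1: what the Bonferroni sentence covers.** Four visits give 4 × 3 / 2 = 6 pairs, each tested at .05 / 6 = .0083. This applies within a measure, between visits. It leaves the group and interaction tests at .05.

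**Step 2: independent measures.** P(at least one of seven significant) = 1 − 0.95^7 = 0.302.

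**Step 3: correlated measures.** The 2 × 4 mixed ANOVA was simulated with no true difference, 20 per arm, within-patient correlation 0.7 between visits, and 100,000 trials per setting.

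| Correlation between measures | At least one of 7 interactions p < .05 |
|---|---|
| 0 | 30.2% |
| 0.3 | 27.4% |
| 0.5 | 23.9% |
| 0.7 | 18.8% |
| 0.9 | 12.3% |

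A separate simulation with 10, 20 or 40 per arm and within-patient correlation 0.6 gave 27.3% to 27.8% at 0.3 and 11.7% to 12.0% at 0.9. The missing sample size therefore hardly matters. Each single test rejected in about 5% of trials.

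**Step 4: sensitivity, at correlations 0.3 and 0.9.** Scores rounded to five levels gave 29.2% and 18.9%. With visits following a first-order autoregressive pattern (0.8) and a Greenhouse-Geisser correction, the rates were 26.6% and 11.3%. Without that correction they were 34.5% and 14.9%, but the single test is then at about 6.6%, so those figures mix a sphericity failure with multiplicity.

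**Step 5: one primary outcome, two change contrasts** (two normal statistics, assumed correlation 0.5). With neither contrast real, at least one is significant in about 9% of trials if each is tested at .05, in about 4.7% with Holm, and in 5.0% in fixed order.

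**Step 6: when may claims on the other six measures open?** Take one primary contrast as real and everything else null, with both contrasts on each of the six measures tested under Holm.

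- Opening them after either primary contrast is significant gives at least one false claim in 7.3% of trials for independent measures when the real contrast has 80% power, and in about 9% with a stronger effect (noncentrality 4). At correlation 0.9 the rates fall to about 4.5% and 5.2%.
- Requiring both primary contrasts keeps the rate at or below 4.8% in every setting.

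The reason is that Holm already passes the full .05 to the second primary contrast once the first is rejected. Opening the other measures at the same moment spends it twice.

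**The case against.** The strongest reply is that the percentages describe a rule the plan never states. It does not say that one significant measure out of seven counts as a program difference, nor that each measure gets its own ANOVA (though that is the natural reading). If all seven results are reported, a reader can see that one stands alone. This stands: the defect is the missing rule, and the rates show what one permitted reading would do.

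A second reply is that the aim is an open comparison with no stated hypothesis or direction, so a confirmatory structure is not the only cure. This also stands. Declaring the trial exploratory would remove the problem without naming a primary outcome. The text makes no such declaration, however, and it sets a significance level for all tests.

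A third is that the omnibus interaction already protects the comparison. It does so only within one measure and only over visits.

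Two stronger readings are tempting. A reader might infer that this trial has a false-positive rate of about 27% or 30%. The documents support no such figure, because they give neither the correlations nor the decision rule. A reader might also infer that no between-group test is planned, or that the individual tests are invalid. Neither follows: group and interaction tests are both planned, and each keeps its 5% level given sphericity.

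**Conclusion.** The point holds as a gap in the decision rule, worth correcting before outcomes are compared by group. Seven measures without a primary outcome, no deciding contrast, and an adjustment limited to time points leave the program comparison without multiplicity control. That much rests on the text alone.

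The size is illustrative: 30% under independence, and about 27% to 12% over assumed correlations of 0.3 to 0.9, given separate ANOVAs, sphericity and an any-significant-interaction reading. Even at 0.9 the rate is more than twice 5%. The figures concern any nominal program difference, not a claim that a particular program is better.

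**What to change.** Before outcomes are compared by group:

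1. Name one primary outcome already collected. The choice is the sponsor's. The upper-extremity Fugl-Meyer motor score is one example, as it is already scored for eligibility ("initial motor part of UE of FMA score ranging from 12 to 56").
2. Define the program comparison on it as the between-group difference in change from pre-treatment to post-treatment (immediate aim) and from pre-treatment to the 6-week follow-up (longer-term aim).
3. Hold the two contrasts together at two-sided .05 with Holm, since the aim does not rank them. If the sponsor ranks them in advance, a fixed order will serve.
4. State that the omnibus group, time and interaction tests, and the Bonferroni time comparisons, are supportive.
5. Report the other six measures as between-group differences in change with 95% confidence intervals and no confirmatory claim. If claims on them are wanted, test them Holm-adjusted only after both primary contrasts are significant.
6. Replace the sentence that puts all tests at .05 with these rules.

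If no confirmatory claim is wanted, declare the trial exploratory and report between-group differences in change with 95% confidence intervals for all seven measures, with no significance-based conclusion.

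**Cost.** Analysis-plan wording and no new data, but some power (correlation 0.5 between contrasts assumed). If only one contrast is real and has 80% power at .05, Holm lowers it to about 71%. Testing at .025 and keeping 80% needs (2.241 + 0.842)² / (1.960 + 0.842)² = 1.21 times the patients. If both are real, Holm gives about 76% each, against 80% and 69% in fixed order. If the effect appears only at follow-up, a fixed order starting at post-treatment finds it in about 3% of trials. The documents give no sample size, so the sponsor must check that the planned number supports the chosen rule. An isolated p < .05 on a secondary scale can no longer be claimed as a positive result.

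### Visit-to-visit changes are tested with single-step Bonferroni, where Holm's step-down procedure gives the same family-wise error control and slightly more power

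*Combined protocol and SAP*

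**What the plan says.** The Methods section sets four visits: "The outcome will be measured at pre-treatment, mid-treatment", "post-treatment, and 6-week follow-up". The Data Analysis section uses a mixed ANOVA to "test the differences within groups across 4 measurement time points (time effect"), and also tests the group effect and the time-by-group interaction. All tests are run "at the $\alpha = .05$ level of significance".

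One sentence takes the time effect down to particular visits: "Pairwise comparison with Bonferroni adjustments is used to examine the differences between measurement time points". It does not say how many pairs are compared, or whether the pairs are formed over both programs together or within each one. It does not extend the adjustment to the group or interaction tests.

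The opening part of the document gives the purpose: "The aims of this study are to determine and compare the immediate and longer-term effects between condensed and distributed programs of RT". Neither immediate nor longer-term is tied to a visit. No sample size, effect size or power is stated.

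**The concern.** Single-step Bonferroni holds every pair to the strictest threshold, even after other pairs have been declared significant. Holm's procedure relaxes the threshold after each rejection and keeps the same family-wise guarantee. Used on the same comparisons, the planned method can therefore miss a real change between visits that Holm would detect, and it offers no better protection against false positives in return.

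At stake is power for change over time, which the plan makes a target through the time effect. A missed pre-to-post or pre-to-follow-up change would be reported as non-significant only because of the choice between two adjustments with equal error control.

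**Working it through.** There is no planned power or per-comparison level to reproduce, so the check starts from the design.

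**Inputs from the document.** Four visits (Methods, Data Analysis); overall level .05 (Data Analysis; two-sided assumed).

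**Assumed inputs.** N = 20 (for example one program alone) or N = 40 (both together); standardised within-patient change d_z of about 0.51 or 0.8; correlation 0.8 between visits; follow-up mean equal to the post-treatment mean.

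**Step 1: thresholds.** Number of pairs = 4 × 3 / 2 = 6.
- Bonferroni: every pair at .05/6 = .0083.
- Holm: order the six p-values from smallest to largest and compare them in turn with .05/6 = .0083, .05/5 = .0100, .05/4 = .0125, .05/3 = .0167, .05/2 = .0250 and .05. Stop at the first failure.

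**Step 2: Holm never rejects fewer.** Any pair with p at or below .0083 passes its Holm threshold, because none of the six is smaller than .0083, and so do all pairs with smaller p-values. Every Bonferroni rejection is therefore also a Holm rejection. This holds for any number of pairs.

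**Step 3: same family-wise error.** Suppose k of the six null hypotheses are true. When Holm reaches the first true one, at most 6 − k hypotheses have been rejected, so its threshold is at most .05/k. The chance that any of the k true nulls has p at or below .05/k is at most k × .05/k = .05. When all six are true, the first step is identical to Bonferroni, so the two error rates are equal. Simulation gave 4.3–4.4% for both.

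**Step 4: size of the loss.** Paired t tests, 20,000 simulated trials per row, power for the pre-to-post contrast (pre-to-follow-up is within about a point):

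| N | d_z | Mid-treatment mean | Bonferroni, 6 pairs | Holm, 6 pairs | Gain (points) |
|---|---|---|---|---|---|
| 20 | 0.51 | halfway to post | 28.5% | 30.0% | 1.5 |
| 20 | 0.51 | equal to post | 28.7% | 30.6% | 1.9 |
| 40 | 0.51 | halfway to post | 67.1% | 69.4% | 2.3 |
| 40 | 0.51 | equal to post | 66.6% | 69.9% | 3.3 |
| 40 | 0.8 | halfway to post | 98.5% | 98.9% | 0.4 |
| 40 | 0.8 | equal to post | 98.6% | 99.1% | 0.5 |

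The gain depends on the time course. If no change has occurred by mid-treatment, more pairs carry a full-sized difference. At d_z 0.51 the gain is then 3.0 points at N = 20 (28.2% to 31.2%) and 5.9 points at N = 40 (66.5% to 72.4%). At d_z 0.8 with N = 20 it runs from 2.8 to 6.2 points over the three time courses.

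**Step 5: a smaller family, for comparison.** Testing only the three pairs among pre-treatment, post-treatment and follow-up gives .05/3 = .0167 per pair. Noncentral-t power with N − 1 degrees of freedom, six pairs v three, both with Bonferroni:
- N = 20, d_z 0.5: 27.3% v 37.3% (10.0 points)
- N = 40, d_z 0.5: 64.9% v 74.3% (9.4 points)
- N = 60, d_z 0.5: 86.9% v 91.7% (4.8 points)
- N = 40, d_z 0.8: 98.6% v 99.3% (0.7 points)

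This gain is larger, but it comes from no longer testing the mid-treatment pairs.

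**Step 6: between-program tests.** The group and interaction tests are at .05 whichever adjustment is used on the visit pairs. Their power changes by zero.

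**The case against.** Bonferroni is valid and conservative, so choosing it is not an error, and the gain from Holm is a few points at most in the main scenarios. The comparison it helps is also uncontrolled: every participant receives BoNT-A and RT, so change from pre-treatment cannot separate the effect of training from that of the toxin or of time. The six-pair family is inferred, and every power figure rests on an assumed N and effect size. All of this stands, and it is why the point is minor. None of it gives a reason to prefer single-step Bonferroni for the tests, because Holm's advantage needs no assumption about N, effect size or number of pairs.

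A reader might infer something stronger: that the trial loses power for the immediate and longer-term effects named in its aim. The documents do not support that. The aim compares those effects between programs. That comparison is carried by the group and interaction terms, which the Bonferroni sentence does not reach. Only the part of the aim that can be read as determining change within patients is touched.

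A reader might also infer that the three pairs involving mid-treatment are wasted because no aim mentions that visit. But mid-treatment is a scheduled assessment, and the document does not define which visits stand for immediate or longer-term. Adjusting for all six pairs buys the right to make claims about all six. Dropping some is a trade-off, not a free gain.

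**Conclusion.** The point holds as a minor improvement to the visit comparisons. On the same six pairs, Holm controls the same family-wise error and never rejects fewer hypotheses, so single-step Bonferroni loses some power for change over time without benefit. The loss is about 1.5 to 3.5 points per contrast at d_z of about 0.51 with N = 20 or 40, when the mid-treatment mean is halfway to the post-treatment mean or equal to it. It is up to about 6 points if no change has occurred by mid-treatment, and under 1 point at d_z 0.8 with N = 40. These sizes rest on the assumed N, effect size, correlation and time course; the direction does not. The randomised comparison between programs is unaffected.

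**What to change.** In the Data Analysis section, name Holm's step-down adjustment in place of Bonferroni for the pairwise visit comparisons. State that it is applied to the unadjusted pairwise p-values for all six pairs at a family-wise level of .05.

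The cost is one phrase in the plan, a short hand calculation for each set of six p-values, and no simple simultaneous confidence intervals that match the Holm decisions.

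Optionally, the sponsor could limit the family to the pairs that represent the immediate and longer-term effects, named in advance. With three pairs this gains about 9 to 10 points at d_z of about 0.5 with N = 20 or 40. It gives up significance tests involving mid-treatment, so it depends on whether the sponsor wants to make claims about that visit.
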